#### 6.6 Proposed types of analyses

Primary efficacy analysis will be intention to treat. Given pragmatic eligibility criteria and up-front one-time treatment, we expect no cross-overs and very few protocol violations. A protected hierarchical analysis plan will be performed. First, non-inferiority will be established if the lower boundary of the 95% confidence interval of the % difference in subjects achieving good outcome (mRS 0-1) in the tenecteplase versus the alteplase arm is greater than -5% (the non-inferiority margin). If non-inferiority is demonstrated, then a test of superiority will be performed as part of secondary analysis. The primary analysis for efficacy will be a stratified Cochran-Mantel-Haenszel (CMH) test where registry (QuICR vs. OPTIMISE) will be used as a stratification variable. If noninferiority is not demonstrated, all subsequent analyses will be considered hypothesis-generating. As sensitivity analysis, logistic regression will be used to provide an adjusted estimate of effect size of the effectiveness of tenecteplase over alteplase. The odds ratio of good 90-day outcome associated with the treatment groups will be estimated using a logistic regression model after adjusting for registry, age, sex, baseline stroke severity and onset-to-needle time. For secondary analyses, frequency tables will be used to summarize binary variables by treatment group. Descriptive statistics will be used to summarize continuous data variables by treatment group. Similar to the primary efficacy variable, binary secondary outcomes will be analyzed using logistic regression analysis. The continuous secondary outcomes will be analyzed using analysis of covariance (ANCOVA) and mixed-effects regression with the registry (QuICR vs. OPTIMISE) variable treated as a randomeffect. If non-inferiority of the primary outcome is demonstrated, a hierarchical multiplicity

adjustment will be used to determine the Type I error for testing the secondary outcomes in order to control the overall familywise type I error rate for the study. Sex will be a unit of analysis. In addition, given previous literature suggesting underutilization of thrombolysis in females, sex-based differences in recruitment, workflow and processes and outcomes will constitute important prespecified subgroup analyses. Details will be provided in the statistical analysis plan that will be developed and reviewed by the trial steering committee.

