## 9. Statistical Analysis

Primary analysis of the trial data to establish non-inferiority will be conducted using risk difference analysis. First, non-inferiority will be established if the lower boundary of the 95% confidence interval of the percentage difference in subjects achieving excellent outcome (mRS 0-1) in the tenecteplase versus the alteplase arm is greater than – 5% (the non-inferiority margin). If non-inferiority is demonstrated, then a test of superiority of tenecteplase vs. alteplase will be performed as part of secondary analysis. In addition, logistic regression will be used to provide an adjusted estimate of the effectiveness of tenecteplase over alteplase for the primary outcome. The risk ratio of good 90-day outcome (mRS01) associated with the treatment groups will be estimated using a mixed-effects logistic regression model that adjusts for age, sex, baseline stroke severity, and stroke onset-to-needle time as fixed effects, and site, and registry (QuiCR vs. OPTIMISE) as random effects.

Secondary analyses will evaluate key safety (mortality and symptomatic intracerebral hemorrhage as defined in the AcT trial MOP) and secondary outcomes using relevant tests of association. Frequency tables will be used to summarize categorical variables by treatment group. Descriptive statistics will be used to summarize continuous data variables by treatment group.

The secondary outcomes and the corresponding analyses are described as follows. Both unadjusted (not described in Table below) and adjusted (described in table below) will be reported. Unadjusted analysis will be tests of difference in proportions, means or medians or regression analysis as appropriate. All analyses will be conducted secondary analyses are conducted at  $\alpha$  = 0.05.

Outcome	Analysis
mRS 0-1 i.e., excellent	Efficacy secondary analysis of the mRS 0-1.
functional outcome (blinded)	Logistic mixed-effects regression model with
	treatment (Tenecteplase vs Alteplase) as
	exposure; age, sex, baseline stroke severity, and
	stroke onset-to-needle time as fixed effects, and
	site, and registry (QuiCR vs. OPTIMISE) as random
	effects.
mRS 0-2 i.e., good functional	Risk difference and the corresponding 95%CI to
outcome (blinded)	assess non-inferiority. Risk ratio and the 95%CI to
	evaluate efficacy

Page 5 of 9

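### The SAP never supplies the testing order that protocol 6.6 promises for the secondary outcomes, so once non-inferiority is met there is no familywise error control beyond mRS 0-1

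*Combined protocol and SAP*

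**What the plan says.** **Protocol 6.6.** The section opens its testing plan with "A protected hierarchical analysis plan will be performed". Non-inferiority on mRS 0-1 comes first, then superiority. If non-inferiority fails, "all subsequent analyses will be considered hypothesis-generating". If it succeeds, a hierarchical procedure is to set the error level at which each secondary outcome is tested, with the stated aim to "control the overall familywise type I error rate for the study". The protocol names no order and no alpha split. It says "Details will be provided in the statistical analysis plan".

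**SAP section 9.** One sequential step appears: "If non-inferiority is demonstrated, then a test of superiority of tenecteplase vs. alteplase will be performed as part of secondary analysis". On the remaining secondary outcomes, the only statement about error rates is the garbled sentence "All analyses will be conducted secondary analyses are conducted at" alpha 0.05. Unadjusted and adjusted analyses are both to be reported, and neither is named as the deciding one. The table has 14 outcome rows. Multiplicity and familywise error are not mentioned, and the protocol's rule for a failed primary is not repeated.

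**The concern.** The protocol states a property of the trial, familywise control over the secondary outcomes, and hands its construction to the SAP. The SAP does not construct it. The hierarchy is therefore specified in neither document.

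The table also leaves room for many tests. Return to pre-stroke status and mRS 0-2 each get a non-inferiority and an efficacy assessment. Each EQ-5D item is analysed separately, alongside a utility index and the visual analogue scale. The SAP labels subgroups and some registry outcomes as exploratory, but gives no such label to mRS 0-2, ordinal mRS, return to pre-stroke status or the EQ-5D measures.

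If non-inferiority is shown, a nominal p below 0.05 on any of these could be presented as protected by a procedure that was never written down. In an open-label trial meant to change practice, an order chosen after the results are known would look data-driven.

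**Working it through.** **Figures in the plan.** The documents state no familywise figure for the secondary outcomes, only the per-test 0.05, so there is none to reproduce. The sample size can be reproduced, which confirms that it rests on the primary test alone. Inputs from SAP section 5 are 35% and 38% with mRS 0-1, a margin of 5 points, one-sided 2.5%, and 90% power.

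- Variance term: 0.35 × 0.65 + 0.38 × 0.62 = 0.4631.
- Distance to the margin: 0.38 − 0.35 + 0.05 = 0.08.
- n per arm = 0.4631 × (1.96 + 1.28)² / 0.08² = 759.6, against the stated 759.
- With 5% loss: 759 / 0.95 = 799 per arm, or about 1600 in total.

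**Counting the secondary tests (SAP section 9 table).**

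- 14 rows: mRS 0-1, six efficacy and patient-reported rows, six safety rows, and EVT use.
- The six efficacy and patient-reported rows are mRS 0-2, ordinal mRS, return to pre-stroke status, EQ5D-VAS, EQ5D-5L and home time. One test per row gives 6.
- Splitting EQ5D-5L into its five listed items plus the utility index, and adding EVT use, gives 4 + 5 + 1 + 1 + 1 = 12 (four single outcomes, five items, utility, home time, EVT).
- Leaving out home time, which may be read as exploratory, and EVT use, which is partly a process measure, gives 10.

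These counts take one test per outcome, although unadjusted and adjusted analyses are both planned.

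**Chance of at least one false positive, all nulls true, two-sided 0.05 each.** Under independence it is 1 − 0.95^k. For correlated tests I used equicorrelated normal statistics. The documents give no correlations, so 0.5 and 0.8 are assumptions chosen to show the range.

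| Tests | Independent | Correlation 0.5 | Correlation 0.8 |
|---|---|---|---|
| 6 | 1 − 0.95^6 = 0.265 | 0.21 | 0.14 |
| 10 | 1 − 0.95^10 = 0.401 | 0.29 | 0.17 |
| 12 | 1 − 0.95^12 = 0.460 | 0.32 | 0.19 |

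**One direction only.** Counting just false claims in favour of tenecteplase (0.025 per test), six tests give 1 − 0.975^6 = 0.141 if independent and about 0.07 at correlation 0.8. The matching target is 0.025.

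**With a fixed sequence.** A familywise error requires rejecting the first true null in the order, which happens with probability at most 0.05 whatever the correlation. Simulation gave about 0.050 at each correlation tried.

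**The case against.** Several points on the other side stand.

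- **Alpha of 0.05 is not itself the fault.** A fixed sequence also tests each step at 0.05. What is missing is the order and the stopping rule.
- **The SAP does contain a gate.** Superiority on mRS 0-1 waits for non-inferiority, as the protocol's hierarchical plan requires. The gap concerns the other secondary outcomes.
- **The higher error rates are the upper part of a range.** Ordinal mRS and mRS 0-2 come from one scale, and return to baseline comes from the same telephone interview, so independence is unrealistic. The count also depends on which rows are treated as claims; safety outcomes are often left outside familywise control.

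A reader might infer that the SAP allows confirmatory claims on secondary outcomes even when non-inferiority fails. The documents do not support that. The protocol makes all later analyses hypothesis-generating in that case, and the SAP's silence does not repeal the rule. Nor does the SAP anywhere call these outcomes confirmatory.

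None of this supplies the missing sequence. After a successful primary test, the protocol requires control across the secondary outcomes and the SAP provides no means of achieving it.

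**Conclusion.** The concern holds in a limited form: followed as written, the plan does not deliver the familywise control that protocol 6.6 states, and the gap opens once non-inferiority has been met. With all nulls true, the chance of at least one nominally significant secondary result is about 14% to 27% for the six efficacy and patient-reported rows, and about 17% to 46% for 10 to 12 tests, against 5%. The ranges rest on my count of the table, one test per outcome, and assumed correlations from 0.8 down to zero. The conclusion does not depend on the exact figure, since every case examined is well above 5%. The one-sided 2.5% primary test, the margin and the sample size of 1600 are untouched. This should be corrected, but it does not threaten the main result.

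**What to change.** 1. Reconcile the secondary outcome lists. Protocol 5.9 includes door-to-needle time, DIDO, mTICI and cognition, which the SAP table omits; the SAP table adds mRS 0-2 and the EQ-5D measures.
2. Write one fixed sequence into SAP section 9: non-inferiority on mRS 0-1 by the planned risk-difference confidence interval, then superiority on mRS 0-1, then a short ordered list. Ordinal mRS, mRS 0-2 and return to baseline function would be one workable order; the choice belongs to the steering committee.
3. Test each step after the non-inferiority gate at two-sided 0.05, name one deciding analysis per secondary step, and stop at the first failure. The deciding analysis for the primary stays the risk difference; an adjusted model must not replace it.
4. Report everything after the stop, and all other outcomes, as estimates with 95% confidence intervals and no claim of significance.
5. Repeat in the SAP that later analyses are hypothesis-generating if non-inferiority fails, and repair the garbled alpha sentence.

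The acceptable alternative is to amend both documents to say that secondary outcomes are supportive and not multiplicity-controlled.

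The sequence needs SAP wording, plus a protocol edit where list reconciliation calls for one; the alternative needs wording in both documents. Neither adds patients or data. The drawback is that fewer secondary results may be called significant. Either change should be made before unblinded analysis.

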# 4. Background

#### 4.1 The Problem

There are two established therapies for acute ischemic stroke, namely intravenous alteplase and endovascular thrombectomy (EVT). The guiding principles behind these therapies are fast, effective and safe reperfusion of ischemic brain. Patients with acute ischemic stroke presenting within 4.5 hours from symptom onset are administered intravenous alteplase. If there is evidence of large vessel occlusion (LVO), these patients are transferred to the nearest comprehensive stroke center (CSC) for EVT. Physicians, hospitals and health systems are focused on implementing efficient triaging systems and workflow processes to improve speed and efficacy of administration of these life-saving therapies. Although efforts over the years with intravenous alteplase administration has resulted in improvement in efficiency metrics like door to needle time (DTN) and door-in-door-out (DIDO) time, these metrics are still not optimal, and the therapy is underutilized. Physicians continue to have concerns about low early reperfusion rates, increased risk of symptomatic intracerebral hemorrhage and challenges with drug administration (bolus + 60-minute infusion) with intravenous alteplase.

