The ATTEST trial was a single-center phase II trial that randomized 104 patients to receive intravenous tenecteplase (0.25 mg/kg body weight) vs. standard dose intravenous alteplase. The primary outcome was the proportion of penumbra salvaged (CT perfusion-defined penumbra volume at baseline minus CT infarct volume at 24–48 h). Despite prognostic imbalances at baseline with more negative imaging features in the tenecteplase group (a higher proportion of patients with large artery occlusion 75% vs. 61% and 33% larger ischemic core volume), there were trends towards earlier major neurological improvement and lower risk of intracranial hemorrhage in patients treated with tenecteplase.

The EXTEND-IA tNK trial (published in early 2018) was another phase II trial with an explanatory framework that enrolled 202 patients with CT-perfusion mismatch and proximal anterior circulation occlusions to receive intravenous tenecteplase (0.25 mg/kg body weight) vs. standard dose intravenous alteplase before being administered standard of care endovascular thrombectomy. The primary outcome (reperfusion of greater than 50% of the ischemic territory or an absence of retrievable thrombus assessed on initial catheter angiopathy assessment before endovascular thrombectomy) occurred in 22% of patients receiving intravenous tenecteplase compared to 10% of patients receiving standard dose intravenous alteplase (rate ratio 2.2; 95% CI, 1.1 to 4.4; P=0.002 for noninferiority, p=0.03 for superiority). In secondary analysis, patients receiving intravenous tenecteplase fared better clinically compared to patients receiving alteplase (median mRS 2 vs. 3, respectively at 90 days, common odds ratio, 1.7; 95% CI, 1.0 to 2.8; p=0.04). The rate of symptomatic intracranial hemorrhage was 1% in both groups. The trial results suggest that by achieving higher earlier recanalization rates, intravenous tenecteplase is potentially capable of achieving better clinical outcomes in patients who are otherwise candidates for endovascular thrombectomy.

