#### 4.6 How will the results of this trial be used?

Results from the proposed trial are likely to provide real life confirmatory evidence about the efficacy of intravenous tenecteplase in patients with acute ischemic stroke eligible for intravenous thrombolysis as per current guidelines. If the

proposed trial demonstrates non-inferiority of intravenous tenecteplase when compared to alteplase, it

is likely to change clinical practice. Given relative ease of administration of tenecteplase (bolus only) vs. alteplase (bolus + infusion), workflow metrics in acute stroke like door-in-door-out (DIDO) time, door to needle (DTN) and door to reperfusion time can all potentially improve, thus improving clinical outcomes. In addition, better reperfusion rates and potentially better safety data is likely to increase utilization of thrombolytic therapy overall while at the same time potentially decreasing the need for resource intensive endovascular thrombectomy in many patients.

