## 7.8 Ancillary Studies, Co-Enrollment and Publication Policy

The trial steering committee will constitute a publication committee that will include site principal investigators and the lead statistician. Policies will be detailed in a Publication Policy Charter. Ancillary studies will also be vetted by the trial steering committee and a decision made on merits of the proposed study.

Patients enrolled in the AcT RRCT are eligible to be enrolled into the EASI-TOC RCT. This study targets a subgroup of patients with ischemic stroke who have what are called tandem occlusions. EASI-TOC aims to determine whether, in addition to thrombectomy to recanalize intracranial occlusion (standard of care); patients with a tandem occlusion should also be acutely treated with a stent to revascularize their cervical internal carotid artery during the thrombectomy procedure. Inclusion in the AcT and EASI-TOC trials do not subject patients to increased risk. No multiplicative biological interaction between the interventions studied in both studies is expected. Patients are randomized just before or at the start of the thrombectomy procedure, once the carotid lesion is

confirmed by angiography. The allocation is 1:1 (stent versus no stent). Both approaches lesion is confirmed by angiography. The allocation is 1:1 (stent versus no stent). Both approaches used in EASI-TOC are considered standard care and used in daily clinical practice. Neither approach is therefore experimental. The pragmatic design of the two studies prevents patients from being subjected to additional study specific investigations, procedures or clinical follow-up beyond usual care.

It is estimated that < 5% of patients eligible for enrolment into the AcT RRCT will also be candidates for EASI-TOC (approximately 60-80 patients out of a planned 1600 patients to be included in AcT). Approximately 1/3rd of subjects eligible for AcT will likely undergo endovascular thrombectomy i.e. 533 subjects.

Statistical simulations with different possible interaction scenarios suggest limited effect on outcomes within both studies. Outcome ascertainment in EASI-TOC does not influence or affect outcome ascertainment in AcT. There are precedents in medicine for including patients in more than one randomized trial, especially in the fields of oncology and critical care and more recently with COVID-19.

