	A Kaplan-Meier survival distribution. Patients alive after 90/120 days were censored. Logistic mixed-effects regression model with treatment (Tenecteplase vs Alteplase) as exposure; age, sex, baseline stroke severity, and stroke onset-to-needle time as fixed effects, and site, and registry (QuiCR vs. OPTIMISE) as random effects.
Symptomatic intracerebral hemorrhage	Risk difference and the corresponding 95%CI
	Logistic mixed-effects regression model with
	treatment (Tenecteplase vs Alteplase) as
	exposure; age, sex, baseline stroke severity, and
	stroke onset-to-needle time as fixed effects, and site, and registry (QuiCR vs. OPTIMISE) as random effects.
Intracranial Hemorrhage on follow-up Imaging (Blinded)	Difference in proportion of ICH categories and the corresponding 95%Cl

Page **7** of **9** 

 
Parenchymal hemorrhage (hemorrhagic infarction type 1, hemorrhagic infarction type 2, parenchymal hematoma type 1, parenchymal hematoma type 2, remote hemorrhagic infarction type 1, remote hemorrhagic infarction type 2, remote parenchymal hematoma type 1, remote parenchymal hematoma type 1, remote parenchymal hematoma type 2)
 
Subdural hemorrhage
 
Subarachnoid hemorrhage
 
Intraventricular
 
	
Peripheral Bleeding requiring Blood Transfusion	Risk difference and the corresponding 95%CI
Angioedema	Risk difference and the corresponding 95%Cl
Proportion of patients receiving EVT	Risk difference and the corresponding 95%CI.
	Logistic mixed-effects regression model with
	treatment (Tenecteplase vs Alteplase) as
	exposure; age, sex, baseline stroke severity, and
	stroke onset-to-needle time as fixed effects, and site, and registry (QuiCR vs. OPTIMISE) as random effects.
Other SAEs and SUSARs	Risk difference and the corresponding 95%CI

Page **8** of **9** 

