#### **10. Subgroup Analyses**

Heterogeneity in treatment effects will be explored via subgroup analyses of pre-specified prognostic variables in the ITT population primarily and in the per-protocol population secondarily. These will include analysis of primary outcome (mRS01) and key safety outcomes by

- a. age (continuous and as < 80 years vs. >= 80 years),
- b. sex (male vs. female),
- baseline stroke severity as measured by the National Institute of Health Stroke Scale (NIHSS; continuous and < 8, 8-15 vs > 15),
- d. presence of large vessel occlusion on baseline CTA
- e. stroke onset-to-needle time (continuous and as <=180 minutes vs. > 180 minutes)
- f. registry (QuiCR vs. OPTIMISE),
- g. type of enrolling hospital (PSCs vs. CSCs),

Evidence of a treatment-by-sub-group variable interaction will be tested by including a multiplicative interaction term (treatment\*subgroup variable) in the model. Subgroup analyses will help to determine if there is efficacy or futility in any pre-specified subgroup. Statistical significance for each subgroup analysis will be exploratory and conducted at  $\alpha = 0.05$ 

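### The comparison of EVT use leaves out large vessel occlusion on baseline CTA, a pre-treatment variable the SAP already plans to use; the planned risk difference is unbiased but less precise than it could be

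*Combined protocol and SAP*

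**What the plan says.** The outcome table in SAP 9 has a row for "Proportion of patients receiving EVT". It plans two analyses. The first is "Risk difference and the corresponding 95%CI", taken over all patients. The second is a mixed-effects logistic model whose fixed effects begin with "exposure; age, sex, baseline stroke severity, and" and end with onset-to-needle time, with site and registry as random effects. LVO is in neither.

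SAP 10 does list "presence of large vessel occlusion on baseline CTA" as subgroup factor d. The outcomes it names are the primary outcome and key safety outcomes, which SAP 9 identifies as mortality and symptomatic intracerebral hemorrhage. EVT is not among them.

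Protocol 4.1 describes how patients come to EVT: "If there is evidence of large vessel occlusion (LVO), these patients are transferred to the nearest comprehensive stroke center (CSC) for EVT". Protocol 7.8 gives the expected rate: "Approximately 1/3rd of subjects eligible for AcT will likely undergo endovascular thrombectomy i.e. 533 subjects". Protocol 4.6 counts among the possible consequences of the results "potentially decreasing the need for resource intensive endovascular thrombectomy in many patients". Protocol 5.3 and SAP 4 balance the randomization by site only. No document gives an LVO share for this trial, an EVT rate by LVO status, a target change in EVT, or power for this outcome.

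**The concern.** If LVO largely decides who can receive EVT, much of the variation in receipt of EVT reflects who had an occlusion at baseline, which the study drug cannot change. An all-patient difference carries that variation as noise, and nothing in the randomization guards against chance imbalance in LVO.

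As an illustration, take LVO in 40% of patients and EVT in 82% with LVO and 1% without (assumptions that give about one third overall). One standard error of LVO imbalance between arms is √(2 × 0.40 × 0.60 / 800) = 0.0245. It moves the crude EVT difference by 0.0245 × (0.82 − 0.01) = 0.020, or 2 points.

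At stake is whether a modest fall in EVT use, one of the hoped-for consequences in protocol 4.6, would show in the trial's own data. Neither the primary non-inferiority conclusion nor safety depends on it.

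**Working it through.** **Inputs from the documents.** 1600 patients, 1:1, so 800 per arm (protocol 6.1, SAP 5). EVT in one third (protocol 7.8). Secondary analyses at α = 0.05 (SAP 9), taken as two-sided to match the 95% interval.

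**Assumptions.** LVO share L from 35% to 77%; EVT rate without LVO, e0, from 0% to 5%; the whole fall occurs in LVO patients. For scale, appendix Table 2 gives LVO shares of 47%, 77% and 100% for three earlier trials. Protocol 4.3.4 gives 75% and 61% for the two arms of one of them.

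**The plan's own figures.** There is no sample size for EVT. For the primary outcome, (1.960 + 1.282)² × (0.35 × 0.65 + 0.38 × 0.62) / 0.08² = 760.3, so 761 per arm against 759 stated. Also 2 × 759 / 0.95 = 1598, and 1600 / 3 = 533. The stated figures reproduce closely.

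**Formulas.** With p = 1/3 and overall fall d, the EVT rate with LVO under alteplase is e1 = [p − (1 − L) × e0] / L. Under tenecteplase it is e1′ = e1 − d/L.

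- Crude SE = √{[p(1 − p) + (p − d)(1 − p + d)] / 800}
- Stratified SE = √{[L × (e1(1 − e1) + e1′(1 − e1′)) + (1 − L) × 2 × e0(1 − e0)] / 800}
- Power = Φ(d / SE − 1.96)

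**Worked example: L = 40%, e0 = 5%, d = 4 points.** e1 = (0.3333 − 0.60 × 0.05) / 0.40 = 0.758 and e1′ = 0.758 − 0.10 = 0.658. Crude SE = √[(0.2222 + 0.2073) / 800] = 0.0232. Stratified SE = √{[0.40 × (0.1833 + 0.2249) + 0.60 × 2 × 0.0475] / 800} = 0.0166. The ratio is 1.40. Crude power is Φ(−0.23) = 41%; stratified power is Φ(0.45) = 67%.

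**Results for a 4-point overall fall (crude power 41% throughout).** The first figure in each cell is for e0 = 0, the second for e0 = 5%.

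| LVO share | EVT with LVO, alteplase | Crude SE / stratified SE | Stratified power |
|---|---|---|---|
| 35% | 95%, 86% | 2.60, 1.59 | 99%, 78% |
| 40% | 83%, 76% | 1.79, 1.40 | 87%, 67% |
| 47% | 71%, 65% | 1.44, 1.26 | 70%, 58% |
| 55% | 61%, 57% | 1.27, 1.17 | 59%, 52% |
| 61% | 55%, 51% | 1.19, 1.12 | 54%, 49% |
| 77% | 43%, 42% | 1.08, 1.05 | 46%, 44% |

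**Crude power for other overall falls.** 3 points 25%, 5 points 58%, 6 points 74%, 6.7 points 83%, 8 points 94%.

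**What the planned severity adjustment recovers.** Simulations of 300 trials per setting, with LVO from 37% to 55%, a 4-point fall and assumed severity distributions, gave an SE about 2% to 10% smaller and power of about 39% to 52% with severity in the model. Adding LVO to severity reduced the SE by a further factor of about 1.2 to 1.8, with power of about 54% to 90%. Site, registry and onset-to-needle time were not simulated.

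**Patients without a CTA.** Suppose 15% have none (an assumption), form their own stratum, and have the overall EVT rate and fall. The variance becomes 0.85 × stratified variance + 0.15 × crude variance. The ratio then drops from 2.60 to 1.91 at L = 35%, e0 = 0; from 1.40 to 1.31 at L = 40%, e0 = 5%; and from 1.05 to 1.04 at L = 77%, e0 = 5%.

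**The case against.** The strongest reply is that nothing here is wrong. Under randomization the all-patient difference is unbiased, and it answers the pragmatic question of how many treated patients go on to EVT. EVT is one of many secondary outcomes, it has no stated power target, and the SAP applies essentially one covariate set across its adjusted models. All of that stands, so this is a matter of efficiency. It does not argue against the change: with 1:1 allocation, a Mantel-Haenszel difference estimates essentially the same all-patient quantity.

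Second, the adjusted model already holds severity, site and registry. Site may carry part of EVT access, since primary stroke centres give thrombolysis only. This stands as a limit on what was tested. The SE ratios describe the risk difference; on the log-odds scale a strong covariate can raise power without shrinking the SE in the same way.

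Third, a pre-treatment CTA is not mandated, because imaging follows standard care (protocol 5.2.2). This also stands and reduces the gain, but did not remove it in the settings tried.

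Two stronger readings are tempting. A reader might infer that the standard error is 1.3 to 2.8 times too large. With no EVT outside LVO and no treatment effect, those ratios correspond to LVO shares of about 55% and 36%, and the upper one needs about 91% of LVO patients to receive EVT. The documents give none of these rates. The ratio shrinks when EVT really falls, and at the 47% and 77% shares tabulated for two earlier trials it is at most about 1.5.

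A reader might also take the reperfusion result that "occurred in 22% of patients receiving intravenous tenecteplase compared to 10% of patients receiving standard dose intravenous alteplase" as a 12-point fall in EVT among LVO patients. That endpoint is reperfusion or absence of retrievable thrombus at the first catheter assessment. Protocol 5.9 lists recanalization at first angiography and receipt of EVT as separate outcomes, and nothing in the documents converts one into the other.

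**Conclusion.** The point holds as a loss of precision in one secondary outcome. Given EVT in one third overall, LVO in 35% to 77%, EVT in 0% to 5% of patients without LVO, and a 4-point overall fall confined to LVO patients, the crude standard error is about 1.05 to 2.6 times the stratified one. Power is about 41% against about 44% to 99%. The gain is large if LVO is only slightly more common than EVT and small if LVO is common. Only the one-third EVT rate comes from the documents; the LVO share, the EVT rate outside LVO and the size of the fall are assumptions.

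A reader might conclude that the planned analysis would often miss any real fall in EVT. That goes too far: crude power is below 60% for overall falls of up to about 5 points, but about 74% at 6 points and higher beyond. Nor is the planned comparison biased or invalid. Severity adjustment probably recovers only a small part of the loss; how much site, registry and onset-to-needle time recover is untested. This is a free or cheap improvement.

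**What to change.** In the EVT row of SAP 9:

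1. Report a Mantel-Haenszel risk difference with 95% interval, stratified by LVO on baseline CTA in three levels: present, absent, no CTA before study drug.
2. Add LVO, coded the same way, as a fixed effect in the logistic model.
3. Keep the all-patient crude proportions and difference alongside.

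The cost is SAP wording, since LVO is already needed for subgroup factor d. There are two downsides: patients without a pre-treatment CTA need their own stratum, which reduces the gain, and the odds ratio becomes conditional on LVO. The stratified risk difference keeps the absolute scale. The change should be fixed before the treatment comparison is seen, so that the choice of covariate cannot be questioned afterwards.
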